8.1. Subject Inclusion Criteria

1. Subject is able to provide written, personally signed, and dated informed consent to participate in the study or will have a legally authorized representative (LAR) sign the informed consent on his or her behalf before completing any study related procedures.
2. Male or female ≥ 18 years of age.
3. Has an established diagnosis of focal or generalized epilepsy or focal and generalized epilepsy with a documented history of predictable seizure episodes that includes at least one of the following:
 - a. Generalized seizure episodes starting with a flurry of absence seizures or myoclonic seizures with a minimum duration of 5 minutes
 - b. Episodes of a prolonged focal seizure with a minimum duration of 3 minutes
 - c. Episodes of multiple (≥ 2) seizures within a 2-hour time period
4. Prior to randomization, has experienced ≥ 4 seizure episodes with predictable pattern during the last 4 weeks (qualification period) and no more than one week without a predictable seizure episode before entry into the in-patient unit.
5. Female participants (if of child-bearing potential and sexually active) and male participants (if sexually active with a partner of child-bearing potential) who agree to use a medically acceptable and effective birth control method throughout the study and for 1 week following the end of the study. Medically acceptable methods of contraception that may be used by the participant and/or his/her partner include abstinence, birth control pills or patches, diaphragm with spermicide, intrauterine device (IUD), surgical sterilization, and progestin implant or injection. Prohibited methods include: the rhythm method, withdrawal, condoms alone, or diaphragm alone.
6. Subject is able to comply by the requirements of the protocol, particularly the requirements and specific Institution policies during the in-patient stay.

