13.2. Endpoints

13.2.1. Efficacy

Primary efficacy endpoint:

The proportion of responders in each treatment group achieving seizure activity cessation within 2 minutes after the administration of the study drug and no recurrence of seizure activity within 2 hours.

Secondary endpoints:

- Seizure episode severity assessed by subject and/or Staff Caregiver
- Use of rescue medication
- Secondary generalization (evolution to a complex partial seizure and/or a generalized tonic-clonic seizure)

Exploratory endpoints:

- Number of seizures during the 4, 6 and 12 hour time periods after study drug administration
- Time to next seizure event with start time >2 minutes after study drug administration

Additional exploratory statistical analyses to further assess for treatment effect will be outlined in the Statistical Analysis Plan finalized prior to database lock for the Primary Efficacy Analysis.

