#### Secondary and Exploratory Efficacy Endpoints

Secondary and exploratory endpoints will be summarized by treatment group and if applicable, by assessment time point. Exploratory statistical testing may be performed if warranted. The Cochran-

Mantel-Haenszel (CMH) test for row-mean score difference will be used to test the treatment difference in the seizure episode severity. The Kruskal-Wallis test will be used to compare seizure frequencies. The time-to-next-seizure data will be summarized and displayed with Kaplan-Meier plots. No multiplicity adjustment will be implemented for exploratory tests.

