**Flags for Efficacy Endpoints:**

- Treatment Response Flag  
= 'Yes', if treated seizure stopped within 2 minutes and there are no seizure events within 2 hours (120 minutes);  
= 'No', otherwise;
- Secondary Generalization Flag  
= 'Yes', if at least one post-treatment seizure event was categorized as "a complex partial seizure" or "partial seizures evolving to secondarily generalized seizures" and/or "a generalized tonic-clonic seizure";  
= 'No', otherwise;
- Number of Post-Treatment Seizures
  - a. N\_4h = # of seizures observed during 0 – 4 hours post-treatment
  - b. N\_6h = # of seizures observed during 0 – 6 hours post-treatment
  - c. N\_12h = # of seizures observed during 0 – 12 hours post-treatment
- Time to the next seizure event  
= the next seizure event start time, if the start time > 2 minutes after study drug dosed  
= censored (left censored at 2 minutes), if the start time ≤ 2 minutes after study drug dosed

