#### 4.1.2 Summary of Efficacy Endpoints

Table 14.2.1.1 Result of Treatment Response – mITT Population

Table 14.2.1.2 Result of Treatment Response – PP Population

Table 14.2.2.1 Results of Seizure Episode Severity Scale – mITT Population

Table 14.2.2.2 Results of Seizure Episode Severity Scale – PP Population

Table 14.2.3.1 Result of Use of Rescue Medication – mITT Population

Table 14.2.3.2 Result of Use of Rescue Medication – PP Population

Table 14.2.4.1 Result of Secondary Generalization Evolution – mITT Population

Table 14.2.4.2 Result of Secondary Generalization Evolution – PP Population

Table 14.2.5.1 Summary of Seizure Number after Study Drug Administration – mITT Population

Table 14.2.5.2 Summary of Seizure Number after Study Drug Administration – PP Population

Table 14.2.5.3 Treatment Comparison of Seizure Number after Study Drug Administration – mITT Population

Table 14.2.5.4 Treatment Comparison of Seizure Number after Study Drug Administration – PP Population

Table 14.2.6.1 Kaplan-Meier Analysis of Time to Next Seizure Event after Study Drug Administration – mITT Population

Table 14.2.6.2 Kaplan-Meier Analysis of Time to Next Seizure Event after Study Drug Administration – PP Population

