#### 4.3 **Figures to be Included in the Clinical Study Report**

- Figure 14.4.1 Kaplan-Meier Plot of Time to Next Seizure Event with Start Time >2 Minutes after Study Drug Administration – mITT Population
- Figure 14.5.1 Plasma PK Concentrations (in Linear Scale) – PK Evaluable
- Figure 14.5.2 Plasma PK Concentrations (in Semi-log Scale) – PK Evaluable

This document cannot be used to support any marketing authorization application and any extensions or variations thereof.

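### SAP 3.6 left-censors at 2 minutes subjects whom the time-to-next-seizure endpoint keeps at risk, and Kaplan-Meier can use those records only after an unstated recoding

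*SAP*

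**What the plan says.** Protocol 13.2.1 lists the exploratory endpoint as "Time to next seizure event with start time >2 minutes after study drug administration", and SAP 2.2.1 repeats it. SAP 3.6 (Flags for Efficacy Endpoints) turns it into a variable with two branches. The first sets the time to "the next seizure event start time, if the start time > 2 minutes after study drug dosed". The second makes the subject "censored (left censored at 2 minutes), if the start time ≤ 2 minutes after study drug dosed". There is no third branch for a subject with no further seizure.

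On analysis, SAP 3.3.1 says "The time-to-next-seizure data will be summarized and displayed with Kaplan-Meier plots". The outputs match: Tables 14.2.6.1 and 14.2.6.2 are titled "Kaplan-Meier Analysis of Time to Next Seizure Event after Study Drug Administration", and Figure 14.4.1 is a "Kaplan-Meier Plot of Time to Next Seizure Event with Start Time >2 Minutes after Study Drug Administration". No method for left-censored or interval-censored data is named. SAP 3.7 declares no change from the protocol's analysis.

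On follow-up, the lead-in to the efficacy criteria in the Protocol synopsis refers to the 12 hours after dosing. Protocol 9.2.3 and 11.5.1 have the Staff Caregiver observing for 24 hours after dosing.

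**The concern.** The endpoint sets a threshold on which seizures count. A seizure starting at or before 2 minutes is simply not the event, and the subject remains under observation for a later one. The SAP branch instead closes that subject's record at 2 minutes.

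Left-censoring is also the wrong kind of record for the planned method. A left-censored time says that the event has already happened by that time. The product-limit estimator has no place for such a record, so a programmer must choose a coding that the SAP does not state. Either obvious choice gives an early seizer a record that differs from the endpoint.

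What is at stake is whether Tables 14.2.6.1 and 14.2.6.2 and Figure 14.4.1 show the endpoint in the figure's title, and whether an analyst's choice is left open until treatment may be known.

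**Working it through.** **Records side by side.** Three subjects, with times in minutes after dosing:

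| Further seizure starts | Endpoint as defined | SAP 3.6, literal | Recoded as event | Recoded as right-censored |
|---|---|---|---|---|
| 1 and 45 | event at 45 | left-censored at 2 | event at 2 | censored at 2 |
| 1 only | right-censored at end of window | left-censored at 2 | event at 2 | censored at 2 |
| none | right-censored at end of window | no value given | – | – |

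No coding of the SAP branch reproduces the endpoint column for either early seizer. In the first row the literal reading also loses the qualifying seizure at 45 minutes.

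**Inputs.** The documents give no figure for this endpoint. The arm size n = 35 is the planned evaluable number in SAP 2.3. It reproduces from that section's primary-endpoint assumptions (57% against 20%, two-sided 0.05, 90% power): the pooled-variance formula without continuity correction gives 35 per arm, with power 90.7% at 35. This confirms n only and has no other bearing here. The following are assumed, because the documents do not supply them: k early starters in an arm, e of them with a later seizure, r recurrences among the other n − k, and everyone followed to one horizon, taken as 12 hours.

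**Estimated recurrence by the horizon.**
- Endpoint as defined: (r + e)/n
- Right-censored at 2 minutes: r/(n − k)
- Event by 2 minutes: (k + r)/n

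**Bounds over all r and e.**
- Event minus endpoint = (k − e)/n, which runs from 0 to k/n.
- Right-censored minus endpoint = rk/[n(n − k)] − e/n. It reaches +k/n at r = n − k, e = 0, and −k/n at r = 0, e = k.
- Event minus right-censored = k/n − rk/[n(n − k)], which runs from 0 to k/n.

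So no two codings differ by more than k/35:
- k = 1: 1/35 = 2.9 points
- k = 2: 2/35 = 5.7 points
- k = 4: 4/35 = 11.4 points
- k = 6: 6/35 = 17.1 points

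**Invented example**, k = 4, e = 3, r = 15:
- endpoint: (15 + 3)/35 = 18/35 = 51.4%
- right-censored: 15/31 = 48.4%
- event: (4 + 15)/35 = 19/35 = 54.3%

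**Scale.** The 95% half-width for one arm of 35 at 50% recurrence is 1.96 × √(0.25/35) = 16.6 points. Even the worst-case shift stays below that until k reaches 6.

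**Can the branch be estimated at all?** Take another invented arm: 7 of 35 start early, 8 of the other 28 recur by 2 hours, and the rest are event-free. The seizure-free estimate at 2 hours is 20/28 = 0.714 if the 7 are right-censored at 2 minutes, and 20/35 = 0.571 if they are coded as events. A self-consistent (Turnbull) estimate that treats them as truly left-censored also gives 0.571, because every left-censored time precedes every observed event. Under the endpoint as defined, the value is anywhere from 20/35 = 0.571 (all 7 seize again by 2 hours) to 27/35 = 0.771 (none does).

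**The case against.** Several stronger readings are tempting, and the documents do not support them.

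- *Kaplan-Meier cannot be run.* It can, once the record is recoded; a true left-censored record here is equivalent to an event by 2 minutes. The difficulty is that the recoding is unstated and that this one counts a start which the endpoint excludes.
- *Later seizures are certainly lost.* That follows only from the literal reading. The first branch could mean the first seizure after 2 minutes, with the second branch kept for subjects whose only further seizure was early; the title of Figure 14.4.1 fits this. Left-censoring could also be loose wording for risk time that begins at 2 minutes. Neither reading rescues the text. On the first, those subjects are event-free after 2 minutes and belong among the right-censored. On the second, an early start should not censor at all.
- *The branch will be used often.* Inclusion criterion 3a admits "Generalized seizure episodes starting with a flurry of absence seizures or myoclonic seizures with a minimum duration of 5 minutes", which may suggest many early starts. But at 2 minutes the Staff Caregiver records whether the treated event has ceased or continues (Protocol 9.2.3, 11.5.1), so a continuing flurry reads as the treated episode still ongoing. The documents do not say whether seizures within a flurry are logged separately.
- *The seizure counts contradict it.* SAP 3.6 counts the number "of seizures observed during 0 – 4 hours post-treatment" with no 2-minute threshold, so a 1-minute start is properly counted there and properly ignored here.
- *Twelve hours is already this endpoint's censoring time.* The synopsis lead-in covers all the efficacy criteria, and observation runs to 24 hours.

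The point about low impact stands. The endpoint is exploratory and displayed without a named test, and Listings 16.8.6 and 16.8.7 should let a reader find affected subjects. The table shells are not in the text available, so a clarifying footnote there cannot be excluded.

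**Conclusion.** Wrong as written, and minor. SAP 3.6 states a rule which, under either available coding, gives early seizers a record that differs from the endpoint. It also leaves subjects with no further seizure without a censoring time. This does not depend on which reading of the first branch is taken; only the loss of a later qualifying seizure does.

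The size is at most k/35 per arm for k early starters. That bound assumes 35 subjects per arm, all followed to a common horizon. Right-censoring can move the estimate either way, while event coding can only raise recurrence. A reader might infer a bias for or against the drug, but with no early-start rate in the documents, overall or by arm, neither its size nor its direction can be stated. The primary endpoint has its own flag in SAP 3.6 and is unaffected, as is the sample size.

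**What to change.** In SAP 3.6, replace the derivation as follows:
- Event time is the start of the first seizure that begins more than 2 minutes after dosing.
- Starts at or before 2 minutes neither count as events nor censor the subject.
- Delete the left-censoring branch.
- Right-censor event-free subjects at the end of the efficacy observation window, or at exit if earlier. The sponsor should confirm the window before unblinding: 12 hours follows the synopsis lead-in, and 24 hours follows the observation period in Protocol 9.2.3 and 11.5.1.
- Report by arm the number of subjects with a seizure start at or before 2 minutes.

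The cost is a few lines in the SAP and the program, plus one count per arm. No new data are needed.

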**Formulas of Metric Conversion:**

- 1 inch = 2.54 cm
- 1 lb = 0.4536 kg
- °C = (°F – 32) x 5/9

**LABORATORY ASSESSMENTS**

**Chemistry (Serum)**

Alanine aminotransaminase  
 Albumin  
 Alkaline phosphatase  
 Amylase  
 Aspartate aminotransaminase  
 Total bilirubin  
 Direct bilirubin  
 Indirect bilirubin  
 Blood urea nitrogen  
 Calcium  
 Carbon dioxide  
 Chloride  
 Creatinine  
 Creatine kinase

**Hematology (Blood)**

Complete blood count  
 Platelet count  
 White blood cell count with differential  
 Hemoglobin  
 Hematocrit

**Urinalysis**

Bilirubin  
 Blood  
 Clarity  
 Urobilirubin  
 Glucose, Urine  
 Ketones

Glucose Lipase Total protein Phosphorus Potassium Sodium Uric Acid	Leukocyte Esterase Nitrate pH Protein, Urine Specific Gravity
--	---

### 3.7 Change to Planned Protocol Analysis

Not applicable.

## 4. OUTPUT PLANNED FOR THE STUDY REPORT (BLINDED PHASE)

### 4.1 Tables to be Included in Study Report

In the following sections, the different results are presented in the order in which it is planned to make them appear in the study report.

The table templates are available in the Appendix of the SAP. The content shown in the templates does only mean as an example. It is not based on real study data or details concerning design.

#### 4.1.1 Summary of Subject Information

Table 14.1.1 Subject Disposition – All Subjects

Table 14.1.2 Summary of Demographics – ITT Population

Table 14.1.3 Summary of Seizure History – ITT Population

Table 14.1.4.1 Summary of Concomitant Medications – Safety Population

Table 14.1.4.2 Summary of Concomitant Procedures – Safety Population

Table 14.1.4.3 Summary of Rescue Medications – ITT Population

#### 4.1.2 Summary of Efficacy Endpoints

Table 14.2.1.1 Result of Treatment Response – mITT Population

Table 14.2.1.2 Result of Treatment Response – PP Population

Table 14.2.2.1 Results of Seizure Episode Severity Scale – mITT Population

Table 14.2.2.2 Results of Seizure Episode Severity Scale – PP Population

Table 14.2.3.1 Result of Use of Rescue Medication – mITT Population

Table 14.2.3.2 Result of Use of Rescue Medication – PP Population

Table 14.2.4.1 Result of Secondary Generalization Evolution – mITT Population

Table 14.2.4.2 Result of Secondary Generalization Evolution – PP Population

Table 14.2.5.1 Summary of Seizure Number after Study Drug Administration – mITT Population

Table 14.2.5.2 Summary of Seizure Number after Study Drug Administration – PP Population

Table 14.2.5.3 Treatment Comparison of Seizure Number after Study Drug Administration – mITT Population

Table 14.2.5.4 Treatment Comparison of Seizure Number after Study Drug Administration – PP Population

Table 14.2.6.1 Kaplan-Meier Analysis of Time to Next Seizure Event after Study Drug Administration – mITT Population

Table 14.2.6.2 Kaplan-Meier Analysis of Time to Next Seizure Event after Study Drug Administration – PP Population

#### **4.1.3 Summary of PK/PD Endpoints**

Table 14.2.7.1 Summary of Plasma PK Concentration by Sample Time Point – PK Population

Table 14.2.7.2 Summary of PK Parameter – PK Population

#### **4.1.4 Summary of Safety Endpoints**

Table 14.3.1.1 Summary of Adverse Events – Safety Set

Table 14.3.1.2 Summary of Adverse Events by MedDRA System Organ Class and Preferred Term – Safety Set

Table 14.3.1.3 Summary of Serious Adverse Events by MedDRA System Organ Class and Preferred Term – Safety Set

Table 14.3.1.4 Summary of Adverse Events by Severity, MedDRA System Organ Class and Preferred Term – Safety Set

Table 14.3.1.5 Summary of Adverse Events by Relationship to Study Agent, MedDRA System Organ Class and Preferred Term – Safety Set

Table 14.3.1.6 Summary of Adverse Events by MedDRA Preferred Term and Overall Frequency – Safety Set

Table 14.3.2.1 Summary of Vital Signs by Time Point – Safety Set

Table 14.3.2.2 Summary of Vital Signs Change from Baseline by Time Point – Safety Set

Table 14.3.3.1 Summary of ECG by Time Point – Safety Set

Table 14.3.3.2 Summary of ECG Change from Baseline by Time Point – Safety Set

Table 14.3.3.3 Summary of ECG Category Results by Time Point – Safety Set

Table 14.3.3.4 Summary of ECG Interpretation by Category and Time Point – Safety Set

Table 14.3.4.1 Summary of Physical Examination by Visit – Safety Set

Table 14.3.4.2 Summary of Neurological Examination by Visit – Safety Set

Table 14.3.5.1 Summary of Laboratory (Hematology) Test Results – Safety Set

Table 14.3.5.2 Summary of Laboratory (Blood Chemistry) Test Results – Safety Set

Table 14.3.5.3 Summary of Laboratory (Urine) Continuous Test Results – Safety Set

Table 14.3.5.4 Summary of Laboratory (Urine) Category Test Results – Safety Set

Table 14.3.5.5 Number and Percentage Subjects with TEPCS Laboratory (Hematology) Test Results – Safety Set

Table 14.3.5.6 Number and Percentage Subjects with TEPCS Laboratory (Blood Chemistry) Test Results – Safety Set

Table 14.3.5.7 Number and Percentage Subjects with TEPCS Laboratory (Urine) Test Results – Safety Set

Table 14.3.5.8 Number and Percentage Subjects with Abnormal Laboratory (Hematology) Test Results – Safety Set

Table 14.3.5.9 Number and Percentage Subjects with Abnormal Laboratory (Blood Chemistry) Test Results – Safety Set

Table 14.3.5.10 Number and Percentage Subjects with Abnormal Laboratory (Urine) Continuous Test Results – Safety Set

Table 14.3.6.1 Summary of Sedation and Alert Scale VAS – Safety Set

Table 14.3.6.2 Summary of Sleepy and Awake Scale VAS – Safety Set

## 4.2 Listings to be Included in the Clinical Study Report

### 4.2.1 Listings of Subject Information

Listing 16.1 Discontinued Subjects – Safety Set

Listing 16.2 Demographic Characteristics – Safety Set

Listing 16.3.1 General Medical History – Safety Set

Listing 16.3.2 Seizure History – Safety Set

Listing 16.4.1 Concomitant Medications – Safety Set

Listing 16.4.2 Concomitant Procedures – Safety Set

Listing 16.4.3 Rescue Medications – Safety Set

Listing 16.5 Study Drug Administration – Safety Set

Listing 16.6 Protocol Deviations – Safety Set

Listing 16.7 Visit Date – Safety Set

### 4.2.2 Listings of Efficacy Data

Listing 16.8.1 Clinical Response – Safety Set

Listing 16.8.2 Seizure Episode Severity Scale – Safety Set

Listing 16.8.3 Use of Rescue Medication – Safety Set

Listing 16.8.4 Secondarily Generalized Evolution – Safety Set

Listing 16.8.5 Number of Post Treatment Seizure – Safety Set

Listing 16.8.6 Post-Treatment Seizure – Safety Set

Listing 16.8.7 Time to Next Seizure Event – Safety Set

### 4.2.3 Listings of PK Data

Listing 16.9.1 Plasma PK Concentrations (unit) – Safety Set

Listing 16.9.2 PK Parameter – Safety Set

### 4.2.4 Listings of Safety Data

Listing 16.10.1 Adverse Events – Safety Set

Listing 16.10.2 Serious Adverse Events – Safety Set

Listing 16.10.3 Severe ( $\geq 3$  CTCAE Grade) Adverse Events – Safety Set

Listing 16.10.4 Study Drug Related Adverse Events – Safety Set

Listing 16.10.5 Adverse Events Leading to Death or Withdrawal – Safety Set

Listing 16.11.1 Results of Laboratory (Hematology) Tests – Safety Set

- Listing 16.11.2 Results of Laboratory (Blood Chemistry) Tests – Safety Set
- Listing 16.11.3 Results of Laboratory (Urine) Tests – Safety Set
- Listing 16.11.4 Results of Urine Drug and Alcohol Tests – Safety Set
- Listing 16.11.5 Results of Urine Pregnancy Tests – Safety Set
- Listing 16.12 Results of Vital Signs – Safety Set
- Listing 16.13 Results of ECG – Safety Set
- Listing 16.14 Abnormalities of Physical Examination – Safety Set
- Listing 16.15 Abnormalities of Neurological Examination – Safety Set
- Listing 16.16 Sedation and Alert VAS – Safety Set
- Listing 16.17 Sleepy and Awake VAS – Safety Set
- Listing 16.18 Randomization List – Safety Set

#### 4.3 **Figures to be Included in the Clinical Study Report**

- Figure 14.4.1 Kaplan-Meier Plot of Time to Next Seizure Event with Start Time >2 Minutes after Study Drug Administration – mITT Population
- Figure 14.5.1 Plasma PK Concentrations (in Linear Scale) – PK Evaluable
- Figure 14.5.2 Plasma PK Concentrations (in Semi-log Scale) – PK Evaluable

This document cannot be used to support any marketing authorization application and any extensions or variations thereof.

## 6. ATTACHMENT: THE SHELLS OF TABLES, FIGURES AND LISTINGS PLANNED FOR CLINICAL STUDY REPORT

This document cannot be used to support any marketing authorization application and any extensions or variations thereof.

REDACTED COPY

7. APPENDIX: COMMON TERMINOLOGY CRITERIA FOR ADVERSE EVENTS (CTCAE, V4.03)

Test	Test Code	Standard Units	Direction of Change	Toxicity Grade				
				0	1	2	3	4
Acidosis	PH	n/a	Decrease/Acidosis	WNL	≥7.3 - <LLN		<7.3	
Activated Partial Thromboplastin Time	APTT	n/a	Increase/Activated partial thromboplastin time prolonged	WNL	>ULN - ≤1.5 xULN	>1.5 xULN - ≤2.5xULN	>2.5 xULN	
Alanine Aminotransferase (ALT/SGPT)	ALT	n/a	Increase/ Alanine aminotransferase increased	WNL	>ULN - ≤3.0 xULN	>3.0 xULN - ≤5.0 xULN	>5.0 xULN - ≤20.0 xULN	>20.0 xULN
Albumin	ALB	g/L	Decrease/Hypoalbuminemia	WNL	≥30 - <LLN	≥20 - <30	<20	
Alkaline Phosphatase	ALP	n/a	Increase/Alkaline phosphatase increased	WNL	>ULN - ≤2.5 xULN	>2.5 xULN - ≤5.0 xULN	>5.0 xULN - ≤20.0 xULN	>20.0 xULN
Alkalosis	PH	n/a	Increase/Alkalosis	WNL	>ULN - ≤7.5		>7.5	
Amylase	AMYLASE	n/a	Increase/Serum amylase increased	WNL	>ULN - ≤1.5 xULN	>1.5 xULN - ≤2.0 xULN	>2.0 xULN - ≤5.0 xULN	>5.0 xULN
Aspartate Aminotransferase	AST	n/a	Increase/Aspartate aminotransferase increased	WNL	>ULN - ≤3.0 xULN	>3.0 xULN - ≤5.0 xULN	>5.0 xULN - ≤20.0 xULN	>20.0 xULN
Bilirubin	BILI	n/a	Increase/Blood bilirubin increased	WNL	>ULN - ≤1.5 xULN	>1.5 xULN - ≤3.0 xULN	>3.0 xULN - ≤10.0 xULN	>10.0 xULN
Calcium	CA	mmol/L	Increase/Hypercalcemia	WNL	>ULN - ≤2.9	>2.9 - ≤3.1	>3.1 - ≤3.4	>3.4
Calcium	CA	mmol/L	Decrease/Hypocalcemia	WNL	≥2.0 - <LLN	≥1.75 - <2.0	≥1.5 - <1.75	<1.5
Calcium Corrected	CACOR	mmol/L	Increase/Hypercalcemia	WNL	>ULN - ≤2.875	>2.875 - ≤3.125	>3.125 - ≤3.375	>3.375
Calcium Corrected	CACOR	mmol/L	Decrease/Hypocalcemia	WNL	≥2.0 - <LLN	≥1.75 - <2.0	≥1.5 - <1.75	<1.5
Calcium Ionized	CAION	mmol/L	Increase/Hypercalcemia	WNL	>ULN - ≤1.5	>1.5 - ≤1.6	>1.6 - ≤1.8	>1.8
Calcium Ionized	CAION	mmol/L	Decrease/Hypocalcemia	WNL	≥1.0 - <LLN	≥0.9 - < 1.0	≥0.8 - < 0.9	<0.8
CD4	CD4	x10E9/L	Decrease/CD4 lymphocytes decreased	WNL	≥0.5 - <LLN	≥0.2 - < 0.5	≥0.05 - <0.2	<0.05

Test	Test Code	Standard Units	Direction of Change	Toxicity Grade				
				0	1	2	3	4
Cholesterol	CHOL	mmol/L	Increase/Cholesterol high	WNL	>ULN - ≤7.75	>7.75 - ≤10.34	>10.34 - ≤12.92	>12.92
Creatine Kinase	CK	n/a	Increase/CPK increased	WNL	>ULN - ≤2.5 xULN	>2.5 xULN - ≤5 xULN	>5 xULN - ≤10 xULN	>10 xULN
Creatinine	CREAT	n/a	Increase/Creatinine increased	WNL	>ULN - ≤1.5 xULN	>1.5 xULN - ≤3.0 xULN	>3.0 xULN - ≤6.0 xULN	>6.0 xULN
Fibrinogen	FIBRINO	umol/L	Decrease/Fibrinogen decreased	WNL	<1.0 - 0.75 x LLN	<0.75 - 0.5 x LLN	<0.5 - 0.25 x LLN	0.25xLLN
Gamma Glutamyl Transferase (GGT)	GGT	n/a	Increase/GGT increased	WNL	>ULN - ≤2.5 xULN	>2.5 xULN - ≤5.0 xULN	>5.0 xULN - ≤20.0 xULN	>20.0 xULN
Glucose (fasting)	GLUC	mmol/L	Increase/Hyperglycemia	WNL	>ULN - ≤8.9	>8.9 - ≤13.9	>13.9 - ≤27.8	>27.8
Glucose	GLUC	mmol/L	Decrease/Hypoglycemia	WNL	≥3.0 - <LLN	≥2.2 - <3.0	≥1.7 - <2.2	<1.7
Glucose (fasting)	GLUC	mmol/L	Increase/Hyperglycemia	WNL	>ULN - ≤8.9	>8.9 - ≤13.9	>13.9 - ≤27.8	>27.8
Glucose	GLUC	mmol/L	Decrease/Hypoglycemia	WNL	≥3.0 - <LLN	≥2.2 - <3.0	≥1.7 - <2.2	<1.7
Glucose (fasting)	GLUC	mmol/L	Increase/Hyperglycemia	WNL	>ULN - ≤8.9	>8.9 - ≤13.9	>13.9 - ≤27.8	>27.8
Glucose	GLUC	mmol/L	Decrease/Hypoglycemia	WNL	≥3.0 - <LLN	≥2.2 - <3.0	≥1.7 - <2.2	<1.7
Granulocytes	GRAN	x10E9/L	Decrease/Neutrophil count decreased	WNL	≥1.5 - <LLN	≥1.0 - <1.5	≥0.5 - <1.0	<0.5
Haptoglobin	HAPTOG	μmol/L	Decrease/Haptoglobin decreased	WNL	>0 - < LLN			
Hemoglobin	HGB	g/L	Increase/Hemoglobin increased	WNL	Increase in >0 - 20 g/L above ULN or above baseline if baseline is above ULN	Increase in >20 - 40 g/L above ULN or above baseline if baseline is above ULN	Increase in >40 g/L above ULN or above baseline if baseline is above ULN	
Hemoglobin	HGB	g/L	Decrease/Anemia	WNL	≥100 - <LLN	≥80 - <100.0	<80	
Leukocytes (WBC)	WBC	x10E9/L	Decrease/White blood cell decreased	WNL	≥3.0 - <LLN	≥2.0 - <3.0	≥1.0 - <2.0	<1.0
Lymphocytes	LYM	x10E9/L	Decrease/Lymphocyte count decreased	WNL	≥0.8 - <LLN	≥0.5 - <0.8	≥0.2 - <0.5	<0.2

Test	Test Code	Standard Units	Direction of Change	Toxicity Grade				
				0	1	2	3	4
Magnesium	MG	mmol/L	Increase/Hypermagnesaemia	WNL	>ULN - ≤1.23		>1.23 - ≤3.30	>3.30
Magnesium	MG	mmol/L	Decrease/Hypomagnesaemia	WNL	≥0.5 - <LLN	≥0.4 - <0.5	≥0.3 - <0.4	<0.3
Neutrophils	NEUT	x10E9/L	Decrease/Neutrophil count decreased	WNL	≥1.5 - <LLN	≥1.0 - <1.5	≥0.5 - <1.0	<0.5
Phosphate (Phosphate, Inorganic)	PHOS	mmol/L	Decrease/Hypophosphataemia	WNL	≥0.8 - <LLN	≥0.6 - <0.8	≥0.3 - <0.6	<0.3
Platelets	PLAT	x10E9/L	Decrease/Platelet count decreased	WNL	≥75.0 - <LLN	≥50.0 - <75.0	≥25.0 - <50.0	<25.0
Potassium	K	mmol/L	Increase/Hyperkalemia	WNL	>ULN - ≤5.5	>5.5 - ≤6.0	>6.0 - ≤7.0	>7.0
Potassium	K	mmol/L	Decrease/ Hypokalemia	WNL		≥3.0 - <LLN	≥2.5 - <3.0	<2.5
Protein (Urine, >16yr)	PROT		Increase/Proteinuria	WNL	1+	2+		
Protein (Urine, ≤16yr)	PROT		Increase/Proteinuria	WNL	1+			
Protein/Creatinine (Urine)	PROTCR T		Increase/Proteinuria	WNL		≥0.5 - ≤1.9	>1.9	
Prothrombin Intl. Normalized Ratio	INR	n/a	Increase/INR increased	WNL	>ULN - ≤1.5 xULN	>1.5 xULN - ≤2.5 xULN	>2.5 xULN	
Sodium	SODIUM	mmol/L	Increase/Hyernatremia	WNL	>ULN - ≤150	>150 - ≤155	>155 - ≤160	>160
Sodium	SODIUM	mmol/L	Decrease/Hyponatremia	WNL	≥130 - <LLN		≥120 - <130	<120
Triacylglycerol Lipase (Lipase)	LIPASE	n/a	Increase/Lipase increased	WNL	>ULN - ≤1.5 xULN	>1.5 xULN - ≤2.0 xULN	>2.0 xULN - ≤5.0 xULN	>5.0 xULN
Triglycerides	TRIG	mmol/L	Increase/Hypertriglyceridemia	WNL	>1.71- ≤3.42	>3.42 - ≤5.7	>5.7 - ≤11.4	>11.4

WNL = Within Normal range, LLN = Lower Limit of Normal Range, ULN = Upper Limit of Normal Range

Statistical Analysis Plan

Study: ENGAGE-E-001

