#### Clinical Laboratory

Clinical laboratory variables will be presented in 3 ways.

1. Change from Baseline to each scheduled assessment will be summarized descriptively. Baseline will be defined as the laboratory value obtained before the first dose of study drug on Day 1; if Day 1 values are unavailable, then values obtained at the Screening Visit will be used.
2. The number and percentage of subjects with abnormal laboratory values will be summarized by treatment group for each clinical laboratory variable.
3. The number and percentage of subjects with treatment-emergent potentially clinically significant (PCS) laboratory values will be summarized by treatment group for each clinical laboratory variable. Potentially clinically significant lab values are defined as those that toxicity grade are  $\geq 3$  from the common terminology criteria for adverse events (CTCAE) criteria (See Section 7 Appendix). Treatment-emergent PCS laboratory values are those in which the baseline value is not PCS and the post-baseline value is PCS.

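### Seven of 21 serum chemistry tests, and hematocrit, have no grade in SAP Section 7, so the treatment-emergent PCS count promised for every laboratory variable cannot work for them, and no other table counts new abnormalities

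*SAP*

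**What the plan says.** SAP 3.3.3, Clinical Laboratory, plans three summaries:

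- Item 1 is the descriptive change from baseline.
- Item 2 is the number and percentage of subjects with abnormal values.
- Item 3 is the number and percentage with treatment-emergent PCS values.

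The scope of item 3 is stated without exception: "laboratory values will be summarized by treatment group for each clinical laboratory variable". Item 2 has the same scope.

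PCS is toxicity Grade 3 or higher "from the common terminology criteria for adverse events (CTCAE) criteria (See Section 7 Appendix". The grading table in Section 7 is headed "APPENDIX: COMMON TERMINOLOGY CRITERIA FOR ADVERSE EVENTS (CTCAE, V4.03". The treatment-emergent rule is: "Treatment-emergent PCS laboratory values are those in which the baseline value is not PCS and the post-baseline value is PCS". Protocol 13.4.4 likewise defines PCS as CTCAE Grade 3 or 4. It plans only two laboratory summaries; the abnormal-value count is added by the SAP.

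The serum panel in SAP 3.6 (the same as Protocol Table 2) lists 21 tests, including "Blood urea nitrogen". The blood outputs are Tables 14.3.5.5 and 14.3.5.6 for PCS and Tables 14.3.5.8 and 14.3.5.9 for abnormal values. One of them is titled "Table 14.3.5.6 Number and Percentage Subjects with TEPCS Laboratory (Blood Chemistry) Test Results – Safety Set".

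**The concern.** A test with no Grade 3 cell cannot produce a PCS value, whatever the result. The SAP nevertheless promises a PCS count for it and gives no rule for displaying it. If the programmed flag defaults to No, the table prints 0% in every arm, and a reader could take a missing criterion for an absence of severe change.

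The abnormal-value count does not fill the gap. It has no baseline condition, so a subject already out of range before dosing is counted along with one who moves out of range afterwards. The ungraded tests therefore have no count of new abnormalities by arm, which is what item 3 sets out to provide.

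**Working it through.** The documents state no figure here, so the check is a line-by-line match of the SAP 3.6 blood tests to Section 7 rows that reach Grade 3.

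| Serum chemistry tests (SAP 3.6) | Number | Section 7 direction reaching Grade 3 | Can be PCS |
|---|---|---|---|
| ALT, alkaline phosphatase, amylase, AST, total bilirubin, creatinine, creatine kinase, lipase | 8 | increase | high only |
| Albumin, phosphorus | 2 | decrease | low only |
| Calcium, glucose, potassium, sodium | 4 | both | high or low |
| Direct bilirubin, indirect bilirubin, blood urea nitrogen, carbon dioxide, chloride, total protein, uric acid | 7 | no row | never |

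- Total: 8 + 2 + 4 + 7 = 21.
- Graded: 8 + 2 + 4 = 14.
- Ungraded: 7/21 = 33%.
- Section 7 has one bilirubin row, code BILI. If it is also applied to the direct and indirect fractions, ungraded tests fall to 7 − 2 = 5, and 5/21 = 24%.

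Hematology:

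- Hemoglobin has an increase row and a decrease row.
- White cells, neutrophils, lymphocytes and platelets have decrease rows only, each with Grade 3 and Grade 4 cells. A platelet count of 25 to below 50 x10E9/L is Grade 3, for example, but no high count has a grade.
- Hematocrit has no row.

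To see what each summary does with an ungraded test, take uric acid and two hypothetical subjects. Subject A is above the upper limit of normal (ULN) at entry and at exit. Subject B is within range at entry and above ULN at exit.

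| Summary | Subject A | Subject B |
|---|---|---|
| Item 3 (treatment-emergent PCS) | cannot count | cannot count |
| Item 2 (abnormal) | counted | counted |
| Item 1 (change from baseline) | absorbed in the arm's summary statistics | absorbed in the arm's summary statistics |
| Treatment-emergent high (proposed) | not counted | counted |

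Only the last row separates the two subjects. Out-of-range values at entry are possible under the eligibility criteria: exclusion criterion 8, for example, removes transaminases only above 2 times ULN.

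**The case against.** The strongest reply is that a test without a CTCAE criterion simply has no PCS definition, and that other outputs cover it:

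- Item 1 gives change from baseline.
- SAP 3.1 presents safety data by treatment group and time point, so item 2 may show entry and exit counts separately.
- Under Protocol 11.8 the investigator classifies post-dose out-of-range results, and under Protocol 13.4.4 clinically significant ones are reported and summarized as adverse events.
- Every hematology and chemistry result is listed (Listings 16.11.1 and 16.11.2).
- Safety is descriptive, after a single dose, with one scheduled post-dose laboratory sample.

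Much of this stands, and it keeps the point small. It does not supply the missing count. Separate entry and exit counts are still marginal: the same number abnormal at both times could be the same subjects or different ones. Adverse event reporting rests on investigator judgement, and listings are not a summary by arm.

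Several stronger readings are tempting but unsupported:

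- A reader might infer that white cells, neutrophils, lymphocytes, platelets and phosphate also show 0% by construction. They do not. Item 3 reports by variable, and low values can reach Grade 3 or 4; only high values are missed.
- A reader might take a printed 0% as certain for the ungraded tests, perhaps as 0 out of the 35 evaluable subjects planned per arm. The SAP gives no display rule and the table shells are not in the text available. The denominator is the Safety Set, which includes the Part 1 subjects.
- A reader might infer that high glucose can never be PCS because its rows are labelled "Glucose (fasting". Those rows have numeric cut-offs that can be applied to any glucose value. Protocol 11.8 leaves sample collection instructions to a separate laboratory document, so the documents do not establish that samples are non-fasting.
- A reader might see a safety signal in the lack of a uric acid grade, because the appended label mentions a weak uricosuric effect. The same label paragraph says no acute renal failure has been attributed to the drug, and creatinine is graded.

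**Conclusion.** The mismatch between item 3 and Section 7 is real and minor. Seven of 21 serum chemistry tests (33%; 5 of 21, or 24%, if the bilirubin row covers the fractions) and hematocrit can never count as PCS. For white cells, neutrophils, lymphocytes, platelets and phosphate, high values go uncounted while low values are covered. For the ungraded tests, no planned summary separates new abnormalities from pre-existing ones.

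The count of seven assumes that BILI means total bilirubin. The fact that ungraded tests cannot be PCS needs no further assumption. A structural 0% in the tables would follow only if the flag defaults to No, which the SAP does not say. The primary efficacy analysis is unaffected.

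**What to change.** In SAP 3.3.3 and the matching table shells:

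1. Change item 2 and Tables 14.3.5.8 and 14.3.5.9 to count treatment-emergent low and treatment-emergent high values for every blood test. Treatment-emergent low means not low at baseline and below the lower limit of normal after dosing. Treatment-emergent high means not high at baseline and above ULN after dosing.
2. Limit item 3 and Tables 14.3.5.5 and 14.3.5.6 to the tests and directions with a Grade 3 cut-off in Section 7, and print *no criterion* for the rest. Say whether the bilirubin row applies to the fractions.
3. For glucose, say whether the fasting row is applied to the samples as collected.

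The first change matters most, because *no criterion* alone would label the gap without filling it. Item 2 is not among the laboratory summaries in Protocol 13.4.4, so redefining it does not conflict with the protocol. Item 1 already requires baseline values, and judging a value abnormal already requires reference ranges. No new data or change in conduct is needed. The cost is SAP wording, minor programming and slightly longer tables that show some tests as not gradable.
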